10.1.2 Serious adverse events

An SAE is defined as any adverse event [appearance of (or worsening of any pre-existing)] undesirable sign(s), symptom(s), or medical condition(s) which meets any one of the following criteria:

- fatal
- life-threatening

Life-threatening in the context of a SAE refers to a reaction in which the participant was at risk of death at the time of the reaction; it does not refer to a reaction that hypothetically might have caused death if it were more severe (please refer to the ICH-E2D Guidelines).

- results in persistent or significant disability/incapacity
- constitutes a congenital anomaly/birth defect
- requires inpatient hospitalization or prolongation of existing hospitalization, unless hospitalization is for:
 - routine treatment or monitoring of the studied indication, not associated with any deterioration in condition
 - elective or pre-planned treatment for a pre-existing condition that is unrelated to the indication under study and has not worsened since signing the informed consent
 - social reasons and respite care in the absence of any deterioration in the participant's general condition
 - treatment on an emergency outpatient basis for an event not fulfilling any of the definitions of a SAE given above and not resulting in hospital admission
- is medically significant, e.g. defined as an event that jeopardizes the participant or may require medical or surgical intervention to prevent one of the outcomes listed above

Medical and scientific judgment should be exercised in deciding whether other situations should be considered serious reactions, such as important medical events that might not be immediately life threatening or result in death or hospitalization but might jeopardize the participant or might require intervention to prevent one of the other outcomes listed above. Such events should be considered as "medically significant." Examples of such events are intensive treatment in an emergency room or at home for allergic bronchospasm, blood dyscrasias, or convulsions that do not result in hospitalization or development of dependency or abuse (please refer to the ICH-E2D Guidelines).

All new malignant neoplasms will be assessed as serious under “medically significant” if other seriousness criteria are not met.

Any suspected transmission via a medicinal product of an infectious agent is also considered a serious adverse reaction.

All reports of intentional misuse and abuse of the product are also considered serious adverse event irrespective if a clinical event has occurred.

10.1.3 SAE reporting

To ensure participant safety, every SAE, regardless of causality, occurring after the participant has provided informed consent and until 30 days after the last study visit must be reported to Novartis safety within 24 hours of learning of its occurrence. MS relapses are exempt from SAE reporting although they may meet the SAE definition on the basis that they are considered medically significant and are frequently associated with hospitalization. These events will be reported on the MS relapse eCRF instead of the SAE form. However, if in the judgement of the Investigator, a MS relapse is unusually severe or unexpected and warrants specific notification, then an SAE form must be completed and submitted according to SAE reporting procedures outlined above. Detailed instructions regarding the submission process and requirements are to be found in the investigator folder provided to each site.

All follow-up information for the SAE including information on complications, progression of the initial SAE and recurrent episodes must be reported as follow-up to the original episode immediately, without undue delay, and under no circumstances later than within 24 hours of the investigator receiving the follow-up information. An SAE occurring at a different time interval or otherwise considered completely unrelated to a previously reported one must be reported separately as a new event.

If the SAE is not previously documented in the Investigator's Brochure or Package Insert (new occurrence) and is thought to be related to the study treatment, a CMO & PS Department associate may urgently require further information from the investigator for health authority reporting. Novartis may need to issue an Investigator Notification (IN) to inform all investigators involved in any study with the same study treatment that this SAE has been reported.

Suspected Unexpected Serious Adverse Reactions (SUSARs) will be collected and reported to the competent authorities and relevant ethics committees in accordance with EU Guidance 2011/C 172/01 or as per national regulatory requirements in participating countries.

Any SAEs experienced after the 30 day period should only be reported to Novartis Safety if the investigator suspects a causal relationship to study treatment.

10.1.4 Pregnancy reporting

Pregnancies

If a female trial participant becomes pregnant, the study treatment should be stopped, and the trial participant must be asked to read and sign pregnancy consent form to allow the Study

Doctor ask about her pregnancy. To ensure participant safety, each pregnancy occurring after signing the informed consent must be reported to Novartis within 24 hours of learning of its occurrence. The pregnancy should be followed up to determine outcome, including spontaneous or voluntary termination, details of the birth, and the presence or absence of any birth defects, congenital abnormalities, or maternal and/or newborn complications.

Pregnancy should be recorded and reported by the investigator to the Novartis Chief Medical Office and Patient Safety (CMO&PS). Pregnancy follow-up should be recorded on the same form and should include an assessment of the possible relationship to the study treatment any pregnancy outcome. Any SAE experienced during pregnancy must be reported.

10.1.5 Reporting of study treatment errors including misuse/abuse

Medication errors are unintentional errors in the prescribing, dispensing, administration or monitoring of a medicine while under the control of a healthcare professional, participant or consumer (EMA definition).

Misuse refers to situations where the medicinal product is intentionally and inappropriately used not in accordance with the protocol.

Abuse corresponds to the persistent or sporadic, intentional excessive use of a medicinal product, which is accompanied by harmful physical or psychological effects.

Study treatment errors and uses outside of what is foreseen in the protocol will be recorded on the appropriate CRF irrespective of whether or not associated with an AE/SAE and reported to Safety only if associated with an SAE. Misuse or abuse will be collected and reported in the safety database irrespective of it being associated with an AE/SAE within 24 hours of Investigator's awareness.

Table 10-1 Guidance for capturing the study treatment errors including misuse/abuse

Treatment error type	Document in Dosing CRF (Yes/No)	Document in AE eCRF	Complete SAE form
Unintentional study treatment error	Yes	Only if associated with an AE	Only if associated with an SAE
Misuse/Abuse	Yes	Yes	Yes, even if not associated with a SAE

For more information on AE and SAE definition and reporting requirements, please see the respective sections.

10.2 Additional Safety Monitoring

Not applicable.

11 Data Collection and Database management

11.1 Data collection

Designated investigator staff will enter the data required by the protocol into the Electronic Case Report Forms (eCRF). The eCRFs have been built using fully validated secure web-enabled software that conforms to 21 CFR Part 11 requirements. Investigator site staff will not be given access to the EDC system until they have been trained. Automatic validation programs check for data discrepancies in the eCRFs, allow modification and/or verification of the entered data by the investigator staff.

The investigator/designee is responsible for assuring that the data (recorded on CRFs) (entered into eCRF) is complete, accurate, and that entry and updates are performed in a timely manner. The Investigator must certify that the data entered are complete and accurate.

After final database lock, the investigator will receive copies of the participant data for archiving at the investigational site.

All data should be recorded, handled, and stored in a way that allows its accurate reporting, interpretation, and verification.

11.2 Database management and quality control

Novartis personnel (or designated CRO) will review the data entered by investigational staff for completeness and accuracy. Electronic data queries stating the nature of the problem and requesting clarification will be created for discrepancies and missing values and sent to the investigational site via the EDC system. Designated investigator site staff are required to respond promptly to queries and to make any necessary changes to the data.

Concomitant treatments and prior medications entered into the database will be coded using the World Health Organization (WHO) Drug Reference List, which employs the Anatomical Therapeutic Chemical classification system. Medical history/current medical conditions and adverse events will be coded using the Medical Dictionary for Regulatory Activities (MedDRA) terminology.

11.3 Site monitoring

Before study initiation, at a site initiation visit or at an investigator's meeting, a Novartis representative will review the protocol and data capture requirements (i.e. eSource DDE or eCRFs) with the investigators and their staff. During the study, Novartis employs several methods of ensuring protocol and GCP compliance and the quality/integrity of the sites' data. The field monitor will visit the site to check the completeness of participant records, the accuracy of data capture / data entry, the adherence to the protocol and to Good Clinical Practice, the progress of enrollment, and to ensure that study treatment is being stored, dispensed, and accounted for according to specifications. Key study personnel must be available to assist the field monitor during these visits. Continuous remote monitoring of each site's data may be performed by a centralized Novartis/delegated CRO/CRA organization. Additionally,

a central analytics organization may analyze data & identify risks & trends for site operational parameters, and provide reports to Novartis clinical teams to assist with trial oversight.

The investigator must maintain source documents for each participant in the study, consisting of case and visit notes (hospital or clinic medical records) containing demographic and medical information, laboratory data, electrocardiograms, and the results of any other tests or assessments. All information on CRFs must be traceable to these source documents in the participant's file. The investigator must also keep the original informed consent form signed by the participant (a signed copy is given to the participant).

The investigator must give the monitor access to all relevant source documents to confirm their consistency with the data capture and/or data entry. Novartis monitoring standards require full verification for the presence of informed consent, adherence to the inclusion/exclusion criteria, documentation of SAEs, and of data that will be used for all primary variables. Additional checks of the consistency of the source data with the CRFs are performed according to the study-specific monitoring plan. No information in source documents about the identity of the participants will be disclosed.

12 Data analysis and statistical methods

Any data analysis carried out independently by the investigator should be submitted to Novartis before publication or presentation.

12.1 Analysis sets

For all analysis sets, participants will be analyzed according to the study treatment(s) received.

The safety analysis set will include all participants that received any study drug.

The efficacy analysis sets at one week, one month, six months, 12 months and 18 months after the second SARS-CoV-2 vaccine and 1, 6 and 12 months after a booster vaccine, respectively, will include all participants who have a valid determination of SARS-CoV-2 reactive T-cells at that time point plus those who failed to receive their second dose of vaccine for whatever reason. The latter will be counted as non-responders. Patients completing vaccination but fail to provide a blood sample at one week after the second vaccination will be excluded from the study and analysis.

12.2 Participant demographics and other baseline characteristics

Demographic and other baseline data including disease characteristics will be listed and summarized descriptively by treatment group (Cohort 1 and 2) for the FAS.

The Safety set will be used for the analyses below. Categorical data will be summarized as frequencies and percentages. For continuous data, mean, standard deviation, median, minimum, and maximum will be presented.

For Cohort 1, the time between second vaccination (cohort 1a) or booster vaccination (cohort 1b) and start of ofatumumab treatment will be presented. For Cohort 2, the time from first ofatumumab dose to first vaccination (cohort 2a) or booster vaccination (cohort 2b) will be summarized. For both cohorts, continuous ofatumumab intake will be presented.

12.3 Treatments

The Safety set will be used for the analyses below. Categorical data will be summarized as frequencies and percentages. For continuous data, mean, standard deviation, median, 25th and 75th percentiles, minimum, and maximum will be presented.

The duration of exposure in days to Ofatumumab will be summarized by means of descriptive statistics using the safety set.

Concomitant medications and significant non-drug therapies prior to and after the start of the study treatment will be listed and summarized according to the Anatomical Therapeutic Chemical (ATC) classification system, by cohort.

12.4 Analysis of the primary endpoint(s)/estimand(s)

The primary clinical question of this study is to estimate the proportion of RMS patients mounting an immune response after receiving a modRNA vaccine (initial vaccination or booster) either before or after starting ofatumumab treatment.

12.4.1 Definition of primary endpoint(s)/estimand(s)

The primary endpoint of this study is the proportion of RMS patients having established SARS-CoV-2-specific T cells as defined by detection of SARS-CoV-2 reactive T-cells, measured by e.g. enzyme-linked immunosorbent spot (ELISpot) assay from T-cells that were stimulated with SARS-CoV-2 peptide mix, one month after second dose of vaccine or one month after booster vaccine in participants who received the respective vaccine before or after starting ofatumumab treatment (yes/no).

12.4.2 Statistical model, hypothesis, and method of analysis

The primary analysis will not use any statistical testing or modelling. The absolute numbers and the proportion of participants with detectable SARS-CoV-2 reactive T-cells within each cohort will be calculated. It will be augmented by a (descriptive) 95% confidence interval (exact Clopper-Pearson).

12.4.3 Handling of remaining intercurrent events of primary estimand

Cohort 1a and cohort 2a: Patients who fail to receive their second dose of vaccine for whatever reason will be included in the analysis as non-responders. Patients who did receive their second dose of vaccine and do not have a valid determination of reactive T-cells to SARS-CoV-2 for whatever reason will be excluded from the analysis of vaccine efficacy.

Patients in cohort 1b and 2b who did receive a booster vaccine and do not have a valid determination of reactive T-cells to SARS-CoV-2 for whatever reason will be excluded from the analysis of vaccine efficacy.

12.4.4 Supportive analyses

Patient demographics and baseline characteristics among both cohorts will be compared in the data analysis. Additionally, patients receiving their initial vaccination (cohorts 1a and 2a) vs. a booster shot (cohort 1b and 2b) will be analyzed separately. If patients received a non-mRNA vaccine as booster, this would be reflected in the analysis.

12.5 Analysis of secondary endpoints/estimands

All secondary endpoints will be summarized descriptively as frequencies and percentages, or, for continuous data, mean, standard deviation, median, minimum, and maximum will be presented.

12.5.1 Safety endpoints

For all safety analyses, the safety set will be used. All listings and tables will be presented by cohort.

Safety summaries (tables, figures) include only data from the on-treatment period with the exception of baseline data which will also be summarized where appropriate (e.g. change from baseline summaries). In addition, a separate summary for death including on treatment and post treatment deaths will be provided. In particular, summary tables for adverse events (AEs) will summarize only on-treatment events, with a start date during the on-treatment period (treatment-emergent AEs).

The on-treatment period lasts from the date of first administration of study treatment to 30 days after the last study visit.

Adverse events

All information obtained on adverse events will be displayed by cohort and participant.

The number (and percentage) of participants with treatment emergent adverse events (events started after the first dose of study medication or events present prior to start of double-blind treatment but increased in severity based on preferred term) will be summarized in the following ways:

- by cohort, primary system organ class and preferred term.
- by treatment, primary system organ class, preferred term and maximum severity.
- by treatment, Standardized MedDRA Query (SMQ) and preferred term.

Separate summaries will be provided for study medication related adverse events, death, serious adverse events, other significant adverse events leading to discontinuation, and adverse events leading to dose adjustment.

A participant with multiple adverse events within a primary system organ class is only counted once towards the total of the primary system organ class.

Vital signs

All vital signs data will be listed by treatment group, participant, and visit/time and if ranges are available, abnormalities (and relevant orthostatic changes) will be flagged. Summary statistics will be provided by treatment and visit/time.

Clinical laboratory evaluations

All laboratory data will be listed by treatment group (cohort 1 and 2), participant, and visit/time and if normal ranges are available abnormalities will be flagged. Summary statistics will be provided by treatment and visit/time.

[REDACTED]

12.7 Interim analyses

The first interim analysis will be performed when at least 5 participants per cohort have completed the study visit one week after a complete SARS-CoV-2 vaccination cycle or on September 1st 2021, whichever comes first.

The second interim analysis will be performed when at least 10 patients in cohort 2 have completed the primary endpoint, 1 month (4 weeks) after the second vaccine (2a) or the booster vaccine (2b) or on January 10th 2022, whichever comes first.

An additional interim analysis will be performed when all participants have completed study visit 1 (one week after SARS-CoV-2 vaccination cycle completion) as this reflects the primary endpoint and whenever deemed necessary. As all analyses in this study are purely descriptive, there is no need for any statistical adjustments.

12.8 Sample size calculation

12.8.1 Primary endpoint(s)

The sample size of 20 participants per arm is selected based on need for early availability of results for the current covid-19 pandemic and the feasibility to recruit sufficient participants. This sample size of 20 subjects will provide estimates of proportion responded with margin of error (half-width of a 95% confidence interval) of 20.1%, 19%, and 17.5% corresponding to response rates of 70%, 75%, and 80%, respectively. Adjusting for 10% drop-out, 22 subjects will be enrolled in each arm. In case of fast recruitment the sponsor is allowed to increase

sample size in each arm by up to 10 additional patients to support the generation of meaningful data in a larger sample size.

13 Ethical considerations and administrative procedures

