2.5.2 Statistical hypothesis, model, and method of analysis

The efficacy analysis set is used for all analyses of the primary parameter.

The primary analysis will not use any statistical testing or modelling. The absolute numbers and the proportion of participants achieving SARS-CoV-2-specific T-cell response within each cohort will be calculated. It will be augmented by a (descriptive) two-sided 95% confidence interval (exact Clopper-Pearson).

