2.15 Interim analysis

See section 1.1 Study design.

3 Sample size calculation

The sample size of 20 participants per arm is selected based on need for early availability of results for the current covid-19 pandemic and the feasibility to recruit sufficient participants. This sample size of 20 subjects will provide estimates of proportion responded with margin of error (half-width of a 95% confidence interval) of 20.1%, 19%, and 17.5% corresponding to response rates of 70%, 75%, and 80%, respectively. Adjusting for 10% drop-out, 22 subjects will be enrolled in each arm. In case of fast recruitment the sponsor is allowed to increase sample size in each arm by up to 10 additional patients to support the generation of meaningful data in a larger sample size.

4 Change to protocol specified analyses

The efficacy analysis set was defined in such a way that it can be applied to all efficacy analyses. With regard to the primary parameter, there is no change in content compared to the definition in the study protocol.

5 Appendix

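### The precision stated for n=20 is a Wald half-width, but the planned interval is exact Clopper-Pearson, which is 1.1 to 1.5 points wider on each side on average and reaches about 24 points below the estimate

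*Protocol*

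**What the plan says.** Protocol 12.8.1 gives the reason for the sample size first: "The sample size of 20 participants per arm is selected based on need for early availability of results", together with recruitment feasibility. It then states what that number delivers, a "margin of error (half-width of a 95% confidence interval) of 20.1%, 19%, and 17.5% corresponding to response rates of 70%, 75%, and 80%, respectively". SAP 3 carries the same statement: "This sample size of 20 subjects will provide estimates of proportion responded with margin of error (half-width of a 95% confidence interval", followed by the same three figures. Neither place names an interval method. On drop-out, Protocol 12.8.1 adds: "Adjusting for 10% drop-out, 22 subjects will be enrolled in each arm".

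The method is named where the primary analysis is described. Protocol 12.4.2 says of the response proportion in each cohort: "It will be augmented by a (descriptive) 95% confidence interval (exact Clopper-Pearson". SAP 2.5.2 specifies the same interval and adds that it is two-sided: "It will be augmented by a (descriptive) two-sided 95% confidence interval (exact Clopper-Pearson". No other interval is planned for the primary proportion.

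**The concern.** The sample size paragraph tells the reader how precise this study's estimates will be, so its figures should describe the interval that the study will report. At n=20 the choice of method matters. The Wald interval is symmetric. With response rates of 70% to 80%, the Clopper-Pearson interval is wider overall and extends further below the estimate than above it, so a single plus-or-minus margin cannot describe it.

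The primary analysis has no test and no model. The proportion and its interval are therefore the whole primary result, and this sentence is the plan's only quantitative statement of what 20 per arm achieves. The study asks whether patients can mount a response, so readers will look mainly at the lower limit, and that is where the stated margin is furthest off. What is at stake is the expected precision only. No conclusion, decision or patient is affected.

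**Working it through.** **Inputs.** n = 20 per arm, planning rates 70%, 75% and 80%, and stated margins 20.1, 19 and 17.5 points (Protocol 12.8.1, SAP 3). Planned interval: two-sided 95% exact Clopper-Pearson (Protocol 12.4.2, SAP 2.5.2). At n=20 the planning rates correspond to 14, 15 and 16 responders.

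**Step 1. Reproduce the plan's figures.** The Wald half-width is 1.96 × √(p(1−p)/n).

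- 70%: 1.96 × √(0.21/20) = 1.96 × 0.10247 = 20.08 points
- 75%: 1.96 × √(0.1875/20) = 1.96 × 0.09682 = 18.98 points
- 80%: 1.96 × √(0.16/20) = 1.96 × 0.08944 = 17.53 points

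These round to the stated 20.1, 19 and 17.5. No other method tried reproduces all three. For 70%, 75% and 80% the half-widths at n=20 are:

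- Wald with continuity correction: 22.6, 21.5, 20.0
- Wilson: 18.7, 17.8, 16.8
- Agresti-Coull: 18.9, 18.2, 17.3
- Jeffreys: 19.1, 18.1, 16.8
- Clopper-Pearson: 21.2, 20.2, 19.0

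**Step 2. Compute the planned interval.** For x responders out of n, the lower limit is the 2.5% quantile of Beta(x, n−x+1) and the upper limit is the 97.5% quantile of Beta(x+1, n−x). The half-width is half the distance between the limits.

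| Responders | Exact limits (%) | Exact half-width | Stated margin | Difference |
|---|---|---|---|---|
| 14/20 (70%) | 45.72-88.11 | 21.19 | 20.1 | 1.09 |
| 15/20 (75%) | 50.90-91.34 | 20.22 | 19 | 1.22 |
| 16/20 (80%) | 56.34-94.27 | 18.96 | 17.5 | 1.46 |

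**Step 3. Compare the limits.** The plan prints no limits. The middle column below is the estimate plus or minus the stated margin, which is the natural reading of a margin of error.

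| Rate | Exact arm below / above | Limits implied by the margin (%) | Implied lower minus exact lower | Implied upper minus exact upper |
|---|---|---|---|---|
| 70% | 24.28 / 18.11 | 49.9-90.1 | 4.18 | 1.99 |
| 75% | 24.10 / 16.34 | 56.0-94.0 | 5.10 | 2.66 |
| 80% | 23.66 / 14.27 | 62.5-97.5 | 6.16 | 3.23 |

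Both implied limits are too high: the lower by 4 to 6 points, the upper by 2 to 3.

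**Step 4. Check how far the result depends on the assumptions.**

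- *Observed count.* Averaging the exact half-width over the binomial distribution, instead of fixing the count at its expected value, gives 20.7, 19.7 and 18.4. The excess over the stated margins falls to about 0.6 to 0.9 points.
- *All 22 enrolled are evaluable.* With fractional counts allowed, the exact half-widths are 20.2, 19.3 and 18.1, an excess of 0.1, 0.3 and 0.6 points. The plan itself expects about 20 evaluable, since 22 × 0.9 = 19.8.
- *Number needed to match.* The exact half-width comes down to the stated margins at about 23 evaluable per arm for 70% and 75%, and about 24 for 80%.
- *Optional increase to 30 per arm.* The exact limits would be 50.6-85.3% for 21/30 and 61.4-92.3% for 24/30, with half-widths of 17.3 and 15.4. The mismatch therefore concerns the figures stated for n=20.

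**The case against.** The best defence is that nothing was miscalculated. The three figures are correct Wald half-widths, the paragraph speaks only of a 95% interval without naming a method, and planning with the normal approximation while reporting an exact interval is common. The plan also defines its margin as a half-width and prints no limits, so the 4-to-6-point shift in the lower limit comes from centring the margin on the estimate. On the quantity actually stated, the gap is 1.1 to 1.5 points, and it is smaller when averaged over possible counts or if more than 20 are evaluable. SAP 2.1 reports percentages as integers, so the half-width gap would show as about one point. Nothing depends on the figure, and Amendment 3 ends recruitment, so a corrected figure can no longer inform enrolment.

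Most of this stands as a limit on the consequence. It does not remove the mismatch. The text states what 20 subjects will provide in this study, and the only interval planned for the primary proportion is Clopper-Pearson. Neither document calls the margins approximate, and two of the three are given to one decimal. The gap stays positive when averaged over counts and with all 22 evaluable. Reading a margin of error as plus or minus around the estimate is what most readers will do, although the limits in Step 3 should be understood as that reading and not as figures the plan prints.

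**Conclusion.** The concern holds and is minor. The stated margins are Wald half-widths at n=20, and the planned Clopper-Pearson interval has half-widths larger by 1.1, 1.2 and 1.5 points at 70%, 75% and 80%. Its asymmetry matters more than its width: the lower limit is about 24 points below the estimate, not 17.5 to 20.1.

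These sizes assume exactly 20 evaluable per arm and 14, 15 or 16 responders, which is the plan's own basis. The half-width gap shrinks under the alternatives in Step 4 and disappears at about 23 to 24 evaluable. The primary analysis itself is unaffected, because the reported interval will be exact whatever the sample size text says.

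**What to change.** In Protocol 12.8.1 and SAP 3, replace the three margins with the exact two-sided 95% Clopper-Pearson limits for n=20 and name the method:

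- 14/20 (70%): 45.7-88.1%
- 15/20 (75%): 50.9-91.3%
- 16/20 (80%): 56.3-94.3%

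Giving limits instead of a margin shows the asymmetry and brings the planning text into line with Protocol 12.4.2 and SAP 2.5.2.

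The cost is text in two places and a slightly less favourable precision statement. Enrolment, analysis and clinical conduct do not change. Under Protocol 14.1 a protocol change needs a written, approved amendment. If no further amendment is planned, correcting SAP 3 alone would still remove the inconsistency within the SAP.
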